7.4.5. Statistical Analyses / Methods

Details of the planned displays are provided in [Appendix 10: List of Data Displays](#) and will be based on GSK data standards and statistical principles.

Unless otherwise specified, endpoints / variables presented in Section [7.4.1](#) will be summarized using descriptive statistics, graphically presented (where appropriate) and listed.

8. SAFETY ANALYSES

The safety analyses will be based on the Safety population, unless otherwise specified.

The summary will be provided by dialysis (ND and PD separately) and treatment group.

8.1. Adverse Events Analyses

Adverse event analyses including the analysis of adverse events (AEs), serious adverse events (SAEs), and other significant AEs will be based on GSK Core Data Standards. The details of the planned displays are provided in [Appendix 10: List of Data Displays](#).

Medical device incidents fulfilling the definition of an AE/SAE will follow the same processes for collecting AE and SAE information and will not be summarized particularly.

Endpoint / Parameter/ Display Type	Absolute		
	Summary		Individual
	T	F	L
Adverse Events (AEs)			
On-therapy AEs by SOC and PT	Y		Y
On-therapy AEs by SOC and PT by Prior ESA Use	Y		
On-therapy AEs by SOC and PT by CKD Stage	Y		
On-therapy AEs by SOC and PT and Maximum Intensity	Y		
On-therapy AEs by SOC and PT and Maximum Intensity by Prior ESA Use	Y		
On-therapy AEs up to Week 4 by SOC and PT	Y		
On-therapy AEs up to Week 4 by SOC and PT by Prior ESA Use	Y		
On-therapy AEs up to Week 4 by SOC and PT by Starting Dose of Daprodustat	Y		
On-therapy AEs up to Week 4 by SOC and PT and Maximum Intensity	Y		
On-therapy AEs up to Week 4 by SOC and PT and Maximum Intensity by prior ESA use	Y		
On-therapy Common ($\geq 2\%$) AEs by SOC and PT by onset	Y		
Post-therapy AEs by SOC and PT	Y		Y
Post-therapy AEs by SOC and PT and Maximum Intensity	Y		
On-therapy Drug-Related AEs by SOC and PT	Y		
On-therapy Drug-Related AEs by SOC and PT by Prior ESA Use	Y		
On-therapy Drug-Related AEs by SOC and PT by CKD Stage	Y		
On-therapy Drug-Related AEs by SOC and PT and Maximum Intensity	Y		
On-therapy Drug-Related AEs up to Week 4 by SOC and PT	Y		
On-therapy Drug-Related AEs up to Week 4 by SOC and PT and Maximum Intensity	Y		
Post-therapy Drug-Related AEs by SOC and PT	Y		
Post-therapy Drug-Related AEs by SOC and PT and Maximum Intensity	Y		
On-therapy Common ($\geq 2\%$) AEs by Overall Frequency	Y	Y ^[1]	
On-therapy Common ($\geq 2\%$) AEs by Overall Frequency by Prior ESA Use	Y		
On-therapy Common ($\geq 2\%$) AEs by Overall Frequency by CKD Stage	Y		

Endpoint / Parameter/ Display Type	Absolute		
	Summary		Individual
	T	F	L
On-therapy Common (>= 5 %) Non-Serious AEs by SOC and PT (Subjects & No. of Occurrences)	Y		
On-therapy Non-Serious Drug Related AEs	Y		
Subject Numbers for Individual AEs			Y
Relationship Between AE SOC, PT & Verbatim Text			Y
Serious and Other Significant AEs			
Fatal Serious AEs			Y
Non-Fatal Serious AEs			Y
On-therapy Serious AEs	Y		Y ^[3]
Post-therapy Serious AEs	Y		
On-therapy Serious Drug Related AEs	Y		
Serious AEs in Screening Period ^[2]			Y
Reasons for Considering as a Serious AE			Y
On-therapy Serious AEs by SOC and PT (Subjects & No. of Occurrences)	Y		
AEs Leading to Withdrawal from Study / Permanent Discontinuation of Study Treatment by SOC and PT	Y		Y
CV Events			Y

NOTES:

- T = Table, F = Figures, L = Listings, Y = Yes display generated, SOC = System Organ Class, PT = Preferred Term.
- Summary = Represents TF related to any summaries (i.e. descriptive statistics) of the observed raw data.
- Individual = Represents FL related to any displays of individual subject observed raw data.

[1] Plot of common AEs and relative risk will be generated by treatment.

[2] Listing will be based on All Screening Population.

[3] Prior ESA use will also be displayed in the listing.

8.1.1. Planned Adverse Events Analyses Displays

- **Adverse Events**

AEs by SOC and PT

The number and percentage of subjects reporting at least one AE will be provided by treatment group. These events will be summarized by primary system organ class and preferred term. On-therapy AEs, on-therapy AEs up to Week 4, and post-therapy AEs will be summarized separately. On-therapy AEs and On-therapy AEs up to Week 4 will also be summarized by prior ESA use. On-therapy AEs will also be summarized by CKD stage. On-therapy AEs up to Week 4 will also be summarized by starting dose of daprodustat (i.e. by cohort, prior ESA use, and baseline Hgb). On-therapy AEs by onset (<=Week 4, >Week 4 to <=Week 16, >Week 16 to <=Week 28, >Week 28 to <=Week 40, >Week 40) will be summarized separately. The number of subjects reporting the first occurrence of each AE will be provided by onset time by primary system organ class and preferred term.

AEs by SOC and PT and Maximum Intensity

AEs will be summarized by treatment group; by maximum intensity (not applicable, mild, moderate, severe), by primary system organ class, and preferred term. Subjects who experience the same event several times with different intensities will only be counted with the maximum intensity in the order of (not applicable < mild < moderate < severe). On-therapy AEs, on-therapy AEs up to Week 4, and post-therapy AEs will be summarized separately. On-therapy AEs and On-therapy AEs up to Week 4 will also be summarized by prior ESA use.

Drug-Related AEs by SOC and PT

The number and percentage of subjects reporting at least one drug-related AE will be provided by treatment group. These events will be summarized by primary system organ class and preferred term. On-therapy AEs, on-therapy AEs up to Week 4, and post-therapy AEs will be summarized separately. On-therapy drug-related AEs will also be summarized by prior ESA use. On-therapy drug-related AEs will also be summarized by CKD stage.

Drug-Related AEs by SOC and PT and Maximum Intensity

Drug-related AEs will be summarized by treatment group; by maximum intensity (not applicable, mild, moderate, severe) by primary system organ class and preferred term. Subjects who experience the same event several times with different intensities will only be counted with the maximum intensity in the order of (not applicable < mild < moderate < severe). On-therapy AEs, on-therapy AEs up to Week 4, and post-therapy AEs will be summarized separately.

On-therapy Common ($\geq 2\%$) AEs by Overall Frequency

The number and percentage of subjects with on-therapy common ($\geq 2\%$ in any treatment group) adverse events by overall frequency will be provided by treatment group. These events will be summarized by preferred term. The summary will also be provided by prior ESA use and CKD stage.

A graph will be produced which displays both AE incidence rates and relative risks for ND subjects.

On-therapy Common ($\geq 5\%$) Non-Serious AEs by SOC and PT (Subjects & No. of Occurrences)

The number and percentage of subjects reporting at least one on-therapy common ($\geq 5\%$ in any treatment group) non-serious AE will be provided by treatment group. The number of on-therapy non-serious AE occurrences will also be provided. These events will be summarized by primary system organ class and preferred term.

On-therapy Non-Serious Drug-Related AEs

The number and percentage of subjects with on-therapy non-serious drug-related AEs will be summarized by preferred term.

- **Serious and Other Significant AEs**

Serious AEs

The number and percentage of subjects reporting at least one serious AE will be provided by treatment group. These events will be summarized by primary system organ class and preferred term. On- and post-therapy serious AEs will be summarized separately.

On-therapy Serious Drug-Related AEs

The number and percentage of subjects with on-therapy serious drug-related AEs will be summarized by preferred term.

On-therapy Serious AEs by SOC and PT (Subjects & No. of Occurrences)

The number and percentage of subjects reporting at least one on-therapy serious AE will be provided by treatment group. The number of on-therapy serious AE occurrences will also be provided. These events will be summarized by primary system organ class and preferred term.

AEs Leading to Withdrawal from Study / Permanent Discontinuation of Study Treatment by SOC and PT

The number and percentage of subjects reporting an on-therapy AE leading to discontinuation of study treatment will be summarized by treatment group. These events will be summarized by primary system organ class and preferred term.

8.2. Adverse Events of Special Interest Analyses

A comprehensive list based on clinical review will be used to identify each type of event. AEs of special interest will be manually-selected before unblinding at patient-level (i.e. following case-by-case review by members of the Safety Review Team (SRT) including representatives from the local Japan team) and not at preferred term level. The details of the planned displays are provided in [Appendix 10: List of Data Displays](#).

Endpoint / Parameter/ Display Type	Absolute		
	Summary		Individual
	T	F	L
AEs of special interest ^[1]			
On-therapy AEs of special interest	Y		Y
Post-therapy AEs of special interest	Y		Y

NOTES:

- T = Table, F = Figures, L = Listings, Y = Yes display generated, SOC = System Organ Class, PT = Preferred Term.
- Summary = Represents TF related to any summaries (i.e. descriptive statistics) of the observed raw data.
- Individual = Represents FL related to any displays of individual subject observed raw data.

[1] Refer to Section [15.6.4](#)

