2.3. Study Design

Overview of Study Design and Key Features	
Screening phase (4 weeks)	Treatment phase (52 weeks) Primary efficacy evaluation period
Follow-up phase (4 weeks)	
Cohort 1 Non-dialysis (ND) subjects	
GSK1278863 group
 
Epoetin beta pegol group

Cohort 2 Peritoneal dialysis (PD) subjects	GSK1278863 group
Cohort 3 Non-dialysis (ND) subjects	
GSK1278863 group
 
Epoetin beta pegol group

Week -4 Week 52	Day 1 Week 56
Week 40	
Design Features	
 • This is a Phase III, open-label, active-controlled, parallel-group, multi-center study to compare the efficacy (verification of noninferiority) and safety of GSK1278863 administered for 52 weeks versus epoetin beta pegol in approximately 286 Japanese ND subjects with renal anemia. • This study also includes an open-label, uncontrolled part to evaluate the efficacy and safety of GSK1278863 in approximately 50 Japanese PD subjects. • Cohort 1 (ND subjects) and Cohort 2 (PD subjects) were set for target population of this study when the study was planned. • Cohort 3 is newly added in amendment (Amendment No. 3). ND subjects will be randomized not to Cohort 1 but to Cohort 3 after amendment No.3.
Dosing	GSK1278863 Starting Dose

Overview of Study Design and Key Features	

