	
(Cohort 1)
 
 • Both ESA non-users and users will start oral treatment with GSK1278863 at the starting dose of 4 mg once daily (Day 1) and remain on the same regimen until the day of Week 4. 
(Cohort 3)
 
 • ESA non-users 
 ○ Baseline Hgb \geq 8.0 g/dL and $<$9.0 g/dL: the subjects will start oral treatment with GSK1278863 at the starting dose of 4 mg once daily (Day 1) and remain on the same regimen until the day of Week 4*. ○ Baseline Hgb \geq 9.0 g/dL and $<$11.0 g/dL: the subjects will start oral treatment with GSK1278863 at the starting dose of 2 mg once daily (Day 1) and remain on the same regimen until the day of Week 4*. • ESA users will start oral treatment with GSK1278863 at the starting dose of 4 mg once daily (Day 1) and remain on the same regimen until the day of Week 4*. 
*: The HemoCue Hgb value will be measured for safety confirmation at Week 2 in ND subjects. When Hgb $>$ 1.0 g/dL increase over 2 weeks, the dose of GSK1278863 is decreased to the next lower dose.
 
(Cohort 2)
 
 • ESA non-users will start oral treatment with GSK1278863 at the starting dose of 4 mg once daily (Day 1) and remain on the same regimen until the day of Week 4. • ESA users will start oral treatment with GSK1278863 at the starting dose of 4 mg once daily (Day 1) and remain on the same regimen until the day of Week 4. 
ESA users should skip ESA on Day 1 when treatment with GSK1278863 is started.
 
Maintenance Dose
 
 • From Weeks 4 to 52, interruption of treatment or dose adjustments will be made within the maintenance dose range of 1-24 mg (Table 6 in the protocol) according to the dose adjustment algorithm (Table 7 in the protocol) to achieve and/or maintain Hgb within the target range (11.0-13.0 g/dL) based on the HemoCue Hgb value measured every 4 weeks. Dose changes will be made every 4 weeks. 
Epoetin Beta Pegol Starting Dose for ESA Non-users
 
 • ESA non-users will start subcutaneous treatment with epoetin beta pegol at a dose of 25 μg once every 2 weeks (Day 1). Dose adjustments will be made within the initial dose range of 25-150 μg (Table 8 in the protocol) according to the dose adjustment criteria (Table 9 in the protocol) to increase Hgb to 11.0 g/dL (lower limit of the target) or more based on the HemoCue Hgb value measured every 4 weeks. Dose changes will be made every 4 weeks. 
Dose Conversion for ESA Users

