3.2. Final Analyses

The final planned primary analyses will be performed after the completion of the following sequential steps:

1. The study has completed with the last subject's last study visit.
2. All required database cleaning activities have been completed and final database release (DBR) and database freeze (DBF) has been declared by Data Management.
3. Randomization codes have been distributed according to RandAll NG procedures.

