15.6.4. Safety

Adverse Events
AE up to Week 4

 • Cut-off date of Week 4 for individuals will be based on Week 4 visit date which is associated with the earliest date throughout Week 4 records (i.e., SDTM.SVSTDTC).
AEs of Special Interest (AESIs)

AESIs are manually-selected at patient-level (i.e. following case-by-case review by members of the SRT including representatives from the local Japan team) and not at preferred term level.
 
AESI categories are classified as follows:
 
 • Thrombosis and/or tissue ischemia secondary to excessive erythropoiesis • Death, myocardial infarction, stroke, heart failure, thromboembolic events, thrombosis of vascular access • Cardiomyopathy • Pulmonary artery hypertension • Cancer-related mortality and tumor progression and recurrence • Esophageal and gastric erosions • Proliferative retinopathy, macular edema, choroidal neovascularization • Exacerbation of rheumatoid arthritis 
Following events will be programmatically identified as AESIs.
 
Thrombosis and tissue ischemia events will be considered to be secondary to excessive erythropoiesis if during the window of [AE start date – 30 days, AE start date +15 days] any one of the following 3 events occurs:
 
 • Any Hgb value > 13 g/dL • Hgb increase > 2 g/dL over 2 weeks (applied to only Cohort 3) • Hgb increase > 4 g/dL over 4 weeks 
Note: Thrombosis and tissue ischemia events that need to be considered against the above 3 Hgb events will be identified by the case-by-case review.
 
Note: HemoCue and central laboratory values will be considered separately. Unscheduled Hgb values will also be used in the assessment of secondary to excessive erythropoiesis if available.
 
Note: All Hgb values that have an assessment date within the window of [AE start date – 58 days, AE start date + 15 days] will be considered.
 
Any SAE which outcome is fatal will be identified AESI as death.

CV Events

Patient profiles of CV events will be provided according to records captured in eCRF, except for Peripheral Arterial Thrombosis Embolism (PAT) form.
 
CV events in PAT form will be provided only when a related AE sequence number is not present. This is because several records in PAT form are captured just for AESI information instead of CV events.

Laboratory Parameters

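### Selecting adverse events of special interest 'before unblinding' does not keep the selection blind to treatment arm in this open-label trial, and the SAP states no other masking

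*SAP*

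**What the plan says.** SAP section 2.3 describes the design: "This is a Phase III, open-label, active-controlled, parallel-group, multi-center study". The arms differ in route and schedule. The test arm receives "oral treatment with GSK1278863 at the starting dose of 4 mg once daily" (one of the starting regimens). In the control arm, "ESA non-users will start subcutaneous treatment with epoetin beta pegol at a dose of" a stated amount, with injections every 2 or every 4 weeks according to prior ESA use and phase of treatment.

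For adverse events of special interest (AESIs), section 8.2 states that "AEs of special interest will be manually-selected before unblinding at patient-level", "following case-by-case review by members of the Safety Review Team (SRT) including representatives from the local Japan team", and not by preferred term. The sentence before it mentions a list based on clinical review, but the SAP does not give that list or say how it relates to the manual step.

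Section 15.6.4 repeats the manual selection without the timing condition and gives the category headings. It then names AESIs identified by program: death, meaning any fatal serious event, and thrombosis or tissue ischemia secondary to excessive erythropoiesis, using three hemoglobin criteria. For the latter, "Thrombosis and tissue ischemia events that need to be considered against the above 3 Hgb events will be identified by the case-by-case review".

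Section 3.2 gives the last step before the final analysis, after database freeze: "Randomization codes have been distributed according to RandAll NG procedures".

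**The concern.** Choosing AESIs case by case requires judgement: whether a borderline event belongs to a category is decided by people. Such a choice compares the arms fairly only if it does not depend on the arm. In a double-blind trial, finishing the work before the blind is broken would secure that. Here no individual-level blind exists to be broken, so the same words carry much less.

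The output is prominent. AESIs are named in the safety endpoint (section 2.2), and Table 3.65 and Listing 44 are in the headline deliverable (section 15.10.3). The categories include myocardial infarction, stroke, thromboembolism, tumor progression and retinopathy. If inclusion leaned one way in one arm, the table would show a difference, or hide one, because of the selection.

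**Working it through.** The SAP gives no figure on this point, so the check sets its sections side by side.

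1. **Is there a blind at patient level?** No. Section 2.3 is explicit, and oral daily treatment differs visibly from injection. Section 15.6.2 derives dose from container numbers (daprodustat) and dosing records (epoetin beta pegol) in the eCRF, so the database identifies the arm before any codes are distributed.

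2. **What could unblinding mean?** The SAP gives no definition. The nearest event is the distribution of codes after database freeze in section 3.2.

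3. **What would that timing protect?** If selection ends before codes and by-arm summaries are released, reviewers cannot steer it by aggregate results. It does not conceal the arm of a single case whose record shows tablets or injections. Concealment needs a masked review package, and the SAP specifies none.

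4. **Which AESIs depend on judgement?**

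| AESI | How identified (section 15.6.4) | Affected? |
|---|---|---|
| Death | Program: any fatal serious event | No |
| Thrombosis or ischemia secondary to excessive erythropoiesis | Hemoglobin rule by program, on candidates chosen by review | Yes, through the candidates |
| Remaining categories | Manual, case by case | Yes |

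5. **Which displays are affected?** Tables 3.65 (on-therapy) and 3.67 (post-therapy) compare arms in ND subjects. Tables 3.66 and 3.68 cover peritoneal dialysis subjects, all on one treatment, so no between-arm contrast exists to distort. The AE and SAE tables by system organ class and preferred term (section 8.1.1) do not use the selection.

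6. **Are the sections consistent?** Section 8.2 describes all AESIs as manually selected; section 15.6.4 does not. The revision history (section 16) confirms that some are not selected by the team.

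7. **Size.** An estimate would need the AESI rate and the number of decisions swayed by knowing the arm. The SAP gives neither. For scale only, assume 286/2 = 143 ND subjects per arm, equal true counts, and three borderline cases left out of one arm. At assumed AESI rates of 5%, 10% and 20% (about 7, 14 and 29 subjects), the ratio moves from 1.00 to 4/7 = 0.57, 11/14 = 0.79 and 26/29 = 0.90. These are assumptions and say nothing about what happened or in which direction.

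**The case against.** A reader might infer that the reviewers see the treatment, that all of them are sponsor staff, and that no protection exists at all. The SAP supports none of these. It does not say what the review package contains or who employs every member, and a protocol or team charter not shown here may cover it. Completing selection before codes are distributed would still limit selection driven by results.

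Nor does the whole safety comparison rest on this step. AESIs are summarized as counts and percentages without a test (section 8.2.1). All AEs and SAEs are tabulated by arm, ophthalmology is summarized separately, profiles of cardiovascular events come from eCRF records, and Listing 36 shows every adverse event. An event left out of the AESI set therefore stays visible. Patient-level selection is also a deliberate choice: tumor progression or worsening of rheumatoid arthritis needs clinical context that a term list may miss. The scenario in the working uses invented rates; at 11/143 versus 14/143 the 95% interval for the ratio is about 0.37 to 1.67, so no inference changes.

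All of this stands and limits the point. It does not supply the missing safeguard: nothing in the SAP keeps the arm from the person judging the case. The full AE tables do not group events into AESI categories, so they are not a like-for-like check on the AESI counts.

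**Conclusion.** The point holds within limits. As written, section 8.2 does not secure selection that is blind to treatment arm for the manually chosen categories in Tables 3.65 and 3.67, including the thrombosis and ischemia candidates. Deaths, the peritoneal dialysis tables and the full AE and SAE tables are unaffected, as is every confirmatory test.

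This is a gap in the stated procedure, not evidence of bias; whether any arises, how large and in which direction, cannot be determined from the SAP. The conclusion assumes that no other document prescribes a masked review. If one does, the SAP should cite it and the point reduces to wording. Otherwise the change should be made, because the table is a headline result and the remedy is cheap.

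**What to change.** - In sections 8.2 and 15.6.4, replace 'before unblinding' with a procedure. The Safety Review Team classifies AESIs from extracts without treatment, dose, route, container, dosing-interval and interruption fields, with drug-revealing text masked where feasible. The classification is locked before exposure data are merged or any by-arm summary is available.
- Keep patient-level selection as the main display. Add one supplementary display for ND subjects, based on a preferred-term list fixed before the review.
- Bring section 8.2 into line with section 15.6.4 on which AESIs are identified by program.

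The cost is SAP wording, preparation of masked extracts and one extra table. Masking of narratives will not be perfect; the fixed-term display gives a check that does not depend on it.

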8.2.1. Planned Adverse Events of Special Interest Analyses Displays

- **AEs of Special Interest (AESIs)**

AEs of Special Interest

The number and percentage of subjects reporting at least one AESI will be provided by treatment group. These events will be summarized by each AESI term (See Section [15.6.4](#)). On-therapy and post-therapy AESIs will be summarized separately.

